15.2. Retention of Records

The PI must maintain all documentation relating to the study for a period of 2 years after the last marketing application approval, or if not approved for 2 years following the discontinuance of the investigational product for investigation. If it becomes necessary for the sponsor's representative or designee, DMID, The Geneva Foundation, or the FDA to review any documentation relating to the study, the investigator must permit access to such records.

Completed, monitored eCRFs will be stored in a secure location by the sponsor's representative or designee. A copy of each completed eCRF will be retained by the investigator.

The PI will be responsible for retaining sufficient information about each subject, ie, name, address, telephone number, and subject identifier in the study, so that the sponsor's representative, the UMB IRB, the FDA, employees of USAMRDC, or other regulatory authorities may have access to this information should the need arise.

It is the policy of the USAMRDC that data sheets are to be completed for all subjects participating in research with an FDA-regulated product for which The Surgeon General, Department of the Army is the sponsor. (Form 60-R, Volunteer Registry Data Sheet). The data sheets will be entered into this Command's Volunteer Registry Database. The information to be entered into this confidential data base includes the subject's name, address, and Social Security Number; study title; and dates of participation. The intent of this data base is twofold: first, to readily answer questions concerning an individual's participation in research sponsored by USAMRDC; and second, to ensure that USAMRDC can exercise its obligation to ensure research subjects are adequately warned (duty to warn) of risks and to provide new information as it becomes available. The information will be stored at USAMRDC for a minimum of 75 years. The Volunteer Registry Database is a separate entity and is not linked to the study database.

16. PUBLICATION POLICY

All data collected during this study will be used to support this IND. USAMRDC will post the trial on www.clinicaltrials.gov. All data may be published in the open medical or military literature with the identity of the subjects protected. Anyone desiring to publish or present data obtained during the conduct of the study will conform to DMID, The Geneva Foundation, Ichor, USAMRIID, and UMB policies and then forward the publication for review to the USAMRDC ORA at [contact] and to the USAMRDC Public Affairs Office at [contact] prior to submission.

APPENDIX A. STUDY PERSONNEL ROLES AND RESPONSIBILITIES

Principal Investigator: The principal investigator (PI) will have overall responsibility for the study and for compliance with the GCP guideline. The PI will conduct the study according to the investigational plan, institutional policies, and all applicable regulations. The PI will comply with the investigator's agreement (FDA 1572), supervise the use of the investigational product, and maintain accurate study records. The PI will permit and comply with audits and monitoring requirements. The PI will report all serious adverse events (SAEs) to appropriate regulatory bodies, as outlined in Section 10.7.

Subinvestigators: Subinvestigators at the clinical site designated by the PI will be responsible for protocol adherence and execution, passage of protocol through local protocol committees, data integrity, applying for and receiving approval for any modifications to the protocol or consent form, ensuring safety of the study subjects, managing and reporting of any AEs, briefing potential subjects, obtaining proper informed consent, determining study eligibility based on screening data and the exclusion criteria, and recording all observations and data in the individual subject records.

Clinical Research Coordinator: The study-site clinical research coordinator is responsible for quality control on all aspects of the study, to include sample collection, volunteer records, source documents and eCRFs, regulatory binders, and datasheets. The coordinator will maintain regulatory files, host visits of auditors, monitor all inspections, coordinate routing of all protocol activity, and maintain and update files of study staff curricula vitae and GCP training certificates.

Research Staff: The research staff will assist in the preparation of the protocol, eCRFs, and other associated documents as needed, monitor various aspects of the study, review information on eCRFs to ensure data are complete and correct, and assist in rectifying discrepancies on eCRFs; maintain study records and logs; assist in evaluating study results and preparing reports; ensure that volunteers have read and understand the informed consent document and have all questions appropriately answered and that informed consent documents are properly signed and dated; collect pre- and post-transfusion vital signs, conduct blood draws, and collect and ensure the integrity of blood samples; collect and record AEs and follow up and consult with physician investigators on all moderate and severe AEs; assist protocol administrator with maintenance of regulatory files and update all study staff curriculum vitae and GCP training certificates.

Clinical Monitor: Study clinical monitoring will be the responsibility of the USAMRDC Clinical Operations and Quality Branch's designated monitor. The clinical monitor will conduct initial, periodic, and termination study site visits; check protocol adherence including adherence with information presented in the informed consent documents, SOPs, and applicable regulations; oversee study file and regulatory documents, cross-check source documents and eCRFs; and observe study procedures.

Clinical Trial Manager: The clinical trial manager coordinates development of the protocol and protocol amendments, coordinates review of the protocol and all protocol-related documents; and coordinates completion of the study start and study close out checklists.

Pharmacovigilance Physician: The pharmacovigilance physician (PVG physician), part of the USAMRDC ORA staff, will serve as the final decision maker in cases where the PI and RM/ISM's review of data results in discordant determinations. In addition, the PVG physician evaluates all SAEs and provides the final determination on relatedness to the product, and

whether expedited reporting is warranted, per current FDA regulation and guidance. The PVG physician is responsible for integrating the review of safety data regarding SAEs and reviewing each SAE report.

Research Monitor/Independent Safety Monitor: The research monitor/independent safety monitor (RM/ISM) oversight position is required by the sponsor per Department of Defense Instruction 3216.02. The RM/ISM, provided by and local to the CVD, is a physician with relevant expertise whose primary responsibility is to provide independent safety monitoring in a timely manner. The RM/ISM will review SAEs in real time and unanticipated problems involving risks to subjects or others.

The RM/ISM is responsible for overseeing the safety of the research and reporting observations/findings to the IRB or a designated institutional official. The RM/ISM will review all unanticipated problems involving risks to subjects or others associated with the protocol and provide an independent report of the event to the IRB. The RM/ISM may discuss the research protocol with the investigators; shall have authority to stop a research protocol in progress, remove individual human subjects from a research protocol, and take whatever steps are necessary to protect the safety and well-being of human subjects until the IRB can assess the RM/ISM's report; and shall have the responsibility to promptly report his or her observations and findings to the IRB or other designated official.

In addition to the responsibilities above the RM/ISM is required to review and provide an unbiased written report for all SAEs and subject deaths to the USAMRDC ORA PSSO (Safety Office) within 24 hours of awareness of the event. The report provided must include, at a minimum, a brief summary of the RM/ISM's review of the event and event outcome, relationship of the event to the investigational product, and whether or not the RM/ISM concurs with the details of the study investigator's report.

Reports of events determined by either the investigator or the RM/ISM to be possibly or definitely related to participation, reports of events definitely related to participation, and reports of events resulting in death should be promptly forwarded to appropriate regulatory bodies; as outlined in Section 10.7.

Clinical Data Manager (sponsor): The sponsor's clinical data manager is responsible for oversight of study eCRF development, database design and validation, and the data management plan.

Clinical Data Manager (study site): The study site clinical data manager is responsible for the development of study eCRFs, database design and validation, data management plan, and data entry into the study database.

Biostatistician: The biostatistician will assist in protocol design and development, design and development of the study database, prepare the study SAP, perform statistical analyses, and review of the study final report.

Product Manager: Responsible for the overall management of the product development effort.

Regulatory Affairs Scientist: Coordinates protocol development and amendments. Conducts regulatory review and obtains IND sponsor representative's approval for study execution. Responsible for submission of the protocol and amendments to the FDA. Responsible for all communications with the FDA.

DMID Medical Officer: The DMID medical officer is a physician who reviews inclusion/exclusion criteria, assesses study design and appropriateness of outcome measures to meet objectives, and provides input from a medical perspective.

[figure not shown]
DMID Medical Monitor: The DMID medical monitor is the physician responsible for reviewing halting rules and safety reports per DMID criteria. The medical monitor generally provides advice regarding safety aspects of the protocol. The medical monitor reviews all serious adverse events and provides input to the Safety Monitoring Committee and Safety Review Committee.

DMID Clinical Project Manager: The clinical project manager ensures that DMID policies are adhered to by the IND holder as it prepares and conducts the trial. This includes meeting DMID and project requirements, facilitating protocol development, and review and/or implementation of the study protocol to promote timely completion.

[figure not shown]
DMID Regulatory Affairs Specialist: The regulatory affairs specialist reviews concepts, protocols, and supporting documentation as required by DMID and the FDA (informed consents, chemistry, manufacturing, and controls section of the IND, etc.) for study feasibility. The regulatory affairs specialist serves as a consultant for product development.

APPENDIX B. SENTINEL SUBJECT ENROLLMENT PROCESS

Randomization Figure pertaining to Amendments 1.0-4.0 (maintained in this document for reference).

Randomization Figure pertaining to Protocol Version 6.0 and future versions. These activities will proceed since completion of enrollment and vaccinations for Groups 2 and 4 and sentinels for Group 6 (n=36 already enrolled by March of 2020). The Randomization Scheme describes plan for enrollment in Nov 2021 of sentinel participants in Group 5 (n=2), then enrollment of Groups 1 and 3 (n=24) and Groups 5 and 6 (n=20).

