The rationale for dosages and plan of routes of IM compared to ID administration in the current Phase 1 study is based on prior work by the delivery device manufacturer (Ichor Medical Systems) and prior experience from the previous HTNV DNA and PUUV DNA vaccine clinical study in which candidate vaccines were shown to elicit antibodies in humans when administered by IM EP. This study affords the opportunity to compare the IM and ID routes of administration, at the highest possible doses, given the limitations of the volumes that can be administered by the IM and ID routes (1 mL and 0.2 mL, respectively). This study is being performed to determine which of IM or ID elicits a superior immune response, given the amount of DNA administered using these routes.

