The first study enrollment activities will involve selection and randomization of volunteers as sentinels for Groups 2 and 4, and then subjects for the remainder of the Group 2 and 4 cohort. The sentinel subjects for Groups 2 and 4 (n = 2 per group, or 4 total) will be vaccinated and evaluated for 48 hours prior to dosing the remainder of Group 2 and 4 (n = 10 per group, or 20 total). After the first dose for all subjects in Groups 2 and 4 has been successfully completed and none of the halting criteria are met, then the first dose will be given to 2 sentinel subjects in Group 6 (n=2 , total of 2 subjects) on the same day, and those 2 subjects will be followed for 48 hours as per the Sentinel Group Halting Rules. The SRC will meet and evaluate the safety data collected in the 48-hour period post-vaccination for sentinels in Group 6. If the SRC finds that the halting rules have been met (Section 6.6.1.1), the PI will notify ORA PSSO within 24 hours. An SMC meeting will be held to conduct a review of clinical and laboratory safety and reactogenicity data. After the meeting, the SMC will make its recommendations in writing regarding continuation, modification, or termination of the clinical trial. If the recommendation is to proceed, enrollment, randomization, and vaccination (Day 0) of the remaining volunteers in Group 6 (n=10 per group). The first dose will be given to 2 sentinel subjects in Group 5 (n=2, total of 2 subjects) on the same day and those 2 subjects will be followed for 48 hours as per the Sentinel Group Halting Rules. The SRC will meet and evaluate the safety data collected in the 48-hour period post vaccination for sentinels in Group 5. If the SRC finds that the halting rules have been met (Section 6.6.1.1) the PI will notify ORA PSSO within 24 hours. A SMC meeting will be held to conduct a review of clinical and laboratory safety and reactogenicity data. After the meeting, the SMC will make its recommendations in writing regarding continuation, modification, or termination of the clinical trial. If the recommendation is to proceed, enrollment, randomization, and vaccination (Day 0) of the subjects in Groups 1 and 3 (n=12 per group, total of 24 subjects) will commence. Subjects in Groups 1 and 3 will be evaluated for the 48-hours post-vaccination for any halting criteria on the Day 2 clinic visit (Table 4). After completion of enrollment and first vaccination for Groups 1 and 3, the remaining subjects for Group 5 and ten Group 6 replacements (total of 20 subjects) may be enrolled, randomized and vaccinated (Day 0), provided that the enrollment of these 20 subjects can be completed within 4 months (see randomization schedule in Appendix B). Subjects are expected to complete a total of 11 visits (not including screening). There will be a 6 month follow-up after the final injection (Day 220). Overall study duration is expected to be approximately 8 months.

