If halting criteria are met after Stage 3, an additional set of 24 participants will be enrolled and equally randomized into Groups 1 or 3 using a permuted block randomization with a block size of 6. Hence a total of 52 participants (12 in Group 1, 12 in Group 2, 12 in Group 3, 12 in Group 4, 2 in Group 5, and 2 in Group 6) will be enrolled in the trial in this scenario.

Stage 4: If no halting criteria are met for Groups 5 and 6 with $n=2$ sentinels per group, then additional 20 subjects will be enrolled and randomized into Groups 5 and 6 ($n=10$ more participants per group, for a total of $n=12$ per group), and an additional set of 24 participants will be enrolled and equally randomized into Groups 1 and 3 at the same time. This is the ideal scenario for workflow and efficiency at CVD.

Trial Enrollment Scenario 4 (N=72):

If halting criteria are not met after Stage 3, an additional set of 40 participants will be equally randomized into Groups 1,3,5 and 6 using a permuted block randomization with a block size of 8 and an additional of 4 participants will be randomized into Group 1 or 3 to achieve a total of 12 participants per group. Hence a total of 72 participants (6 groups, 12 per group) will be enrolled in the trial in this scenario.

A single document delineating the randomized assignment of subjects to vaccine groups for various scenarios described above will be pre-generated by the study statistician and maintained in a secure location as part of the regulatory file. During the study, investigators, research coordinators, University of Maryland's IDS, representatives of the sponsor and applicable regulatory authorities will have access to this list if required by their duties.

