- Any laryngospasm, bronchospasm, or anaphylaxis within 1 day after administration of study product that is considered related to study product.
- Any generalized urticaria within 3 days after administration of study product that is considered related to study product.
- Serious adverse event related to the study vaccination.
- As deemed necessary by the site principal investigator or appropriate sub-investigator for noncompliance or other reasons.
- Subject refusal of further study vaccination.
- Termination of this trial.
- New information becomes available that makes further administration of the study vaccine unsafe.

All data collected up to the time of withdrawal, including any final evaluation and lab results that may be pending at the time of withdrawal, will be included in the final analysis. All major comparisons between randomized groups will be according to “intent-to-treat” (ITT) principle, that is, participants will be analyzed (and outcomes attributed) according to randomized strategy, regardless of subsequent treatment.

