9. IMMUNOGENICITY

Descriptive analysis of immunogenicity outcomes will include all subjects who meet the eligibility criteria, received at least one vaccination, and for whom serological data is available. The primary analysis variable is the proportion of seropositive subjects ($\text{PsVNA50} \geq 1:20$) at each scheduled time point (e.g., Days 0, 28, 56, 84, 140, and 220) (Table 3.1), and the final overall rate of seroconversion over these timepoints. Additionally, the proportion of subjects to ever reach seropositivity will be provided at each scheduled time point for which blood samples are taken (Table 3.2). Duration of seropositivity is presented in Table 3.3. For each study group, a binomial proportion, and corresponding 95% CI will be calculated. Chi-squared test or Fisher's exact test will be used to examine the association between group and each binary outcome of interest. Figures 1.1 and 1.2 will present percentages of subjects with seropositivity and seroconversion, by time point by group.

The secondary analysis variable is geometric mean titers, with 95% CIs, of the PsVNA50 for HTNV and PUUV specific antibodies at each scheduled time point (e.g., Days 0, 28, 56, 84, 140, and 220), and will be presented in Figure 1.5. Geometric mean titers, standard errors, and 95% CIs will be calculated using log-transformed titers, titers below the lower limit of detection (<20) will be transformed to a value equal to the lower limit of detection divided by the square root of 2 ($20/\sqrt{2} = 14.1$ Hornung & Reed (1990) (Table 3.4). PsVNA80 titers may be calculated from existing data for information. The reciprocal of the dilution that results in an 80% decrease in luciferase activity is the PsVNA80 titer. PsVNA using other hantavirus PsV (eg, Seoul virus, Dobrava virus) may also be performed to evaluate levels of cross-neutralizing antibodies. Additionally, Fisher's exact test will be used to examine the difference in the proportion of participants to ever seroconvert between each two groups (Table 4.3).

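### Six of the seven planned route and combination contrasts compare groups that share no enrolment stage, and the SAP tests them as randomized comparisons without a caveat

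*Protocol*

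**What the plan says.** Protocol 6.2 sets the order of enrolment. Groups 2 and 4 come first (sentinels, then the rest), then Group 6, then two Group 5 sentinels, then Groups 1 and 3. The last stage is conditional: "After completion of enrollment and first vaccination for Groups 1 and 3, the remaining subjects for Group 5 and ten Group 6 replacements" may be enrolled and randomized if those 20 can be completed within four months. Appendix B supplies the dates. It reports "n=36 already enrolled by March of 2020" and plans "enrollment in Nov 2021 of sentinel participants in Group 5 (n=2), then enrollment of Groups 1 and 3 (n=24"), then 20 across Groups 5 and 6.

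The purpose of the comparisons is explicit. Protocol 4.2 states "This study is being performed to determine which of IM or ID elicits a superior immune response". The two secondary objectives (Protocol 5.2, SAP 3.2) are combination versus monovalent, and the most immunogenic combination and route.

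SAP v4.0 is dated January 2019. In its 4.2.1, Scenario 4, "an additional set of 40 participants will be equally randomized into Groups 1,3,5 and 6", a scheme that Version 6.0 no longer follows. SAP 4.7 says "All major comparisons between randomized groups will be according to" the intention-to-treat principle. SAP 9 says Fisher's "exact test will be used to examine the difference in the proportion of participants to ever seroconvert between each two groups". Table 4.3 lists the pairs as 1v2, 3v4, 5v6, 1v5, 3v5, 2v6 and 4v6, each with a two-sided p-value. There is no stage term, no restriction to concurrent participants and no footnote on timing.

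**The concern.** Random allocation protects a comparison only when the participants compared could have been assigned to either group. Where two groups are filled in separate stages, any difference between them also carries whatever changed in between: who was recruited, season, pandemic conditions, age of the product lots. Both secondary objectives rest on the Table 4.3 contrasts. If most of them set one enrolment period against another, a reported difference, or its absence, cannot be credited to route or to mixing the vaccines as a randomized result could be. A reader of the final tables would not learn this from the SAP.

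**Working it through.** **Step 1. Reproduce the enrolment total.** Appendix B gives 36 by March 2020, then 2, 24 and 20. 36 + 2 + 24 + 20 = 82, which matches the protocol maximum and also equals 72 + 10. Appendix B's wording is "sentinels for Group 6 (n=36 already enrolled by March of 2020". Two Group 6 sentinels would give 12 + 12 + 2 = 26, so 36 is read as 12 + 12 + 12, with all the original Group 6 subjects enrolled by then.

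**Step 2. Stages under Version 6.0 (Protocol 6.2, Appendix B).**

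| Stage | Groups (n) | Timing |
|---|---|---|
| A | 2 (12), 4 (12) | by March 2020 |
| B | 6 (12) | after A, by March 2020 |
| C | 5 sentinels (2) | from Nov 2021 |
| D | 1 (12), 3 (12) | after C |
| E, optional | 5 (10), 6 (10) | after D |

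Stages B and C each contain one group, so nothing is randomized between groups within them.

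**Step 3. Concurrent participants per pair.** For each pair, add up the participants of each group enrolled in a stage that contains both groups. The SAP column applies the same count to SAP 4.2.1, Scenario 4.

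| Pair | In Table 4.3? | Version 6.0 | SAP scheme |
|---|---|---|---|
| 1v2 | yes | 0 | 0 |
| 3v4 | yes | 0 | 0 |
| 2v6 | yes | 0 | 0 |
| 4v6 | yes | 0 | 0 |
| 1v5 | yes | 0 | 10 v 10 |
| 3v5 | yes | 0 | 10 v 10 |
| 5v6 | yes | 10 v 10 of 12 v 22 | 12 v 12 |
| 2v4 | no | 12 v 12 | 12 v 12 |
| 1v3 | no | 12 v 12 | 12 v 12 |

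Under Version 6.0, six of the seven tested pairs have no concurrent participants. In 5v6, 20 of 34 are concurrent; the other 14 are the 12 original Group 6 subjects and the two Group 5 sentinels. If stage E is not run, the count becomes seven of seven. The two fully co-randomized pairs are not tested.

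**Step 4. Time gaps.**
- 1v2 and 3v4: from the end of March 2020 to the start of November 2021 is 19 months at least.
- 2v6 and 4v6: consecutive stages before March 2020 for the original 12 in Group 6; at least 19 months for the ten replacements.
- 1v5 and 3v5: adjacent stages, with the two sentinels before Groups 1 and 3 and the other ten after.

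**Step 5. What a period shift would do.** The documents give no period effect and no titer SD, so every input here is assumed. There is no true vaccine effect, and 12 v 12 is used, as in 1v2 and 3v4.

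Seroconversion: the rejection rate is the sum, over all pairs of counts x and y, of Bin(x; 12, p1) × Bin(y; 12, p2) wherever the two-sided Fisher p is 0.05 or less.
- 75% v 75%: 1.5%. 75% v 50%: 14.3%.
- Centered on 50%, shifts of 0, 10, 20 and 30 points: 2.3%, 4.0%, 9.7%, 21.1%.

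GMT ratio: a 2-fold drift is 0.3 log10. The noncentrality is 0.3 / (SD × √(2/12)), with 22 df and critical t = 2.074.
- SD 0.6: noncentrality 1.22; the nominal 95% CI misses the true ratio 21.6% of the time.
- SD 0.4: noncentrality 1.84; it misses 42.0% of the time.

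**The case against.** The strongest reply is that this is a Phase 1 trial with a safety primary objective. The combination objective is labelled preliminary, Protocol 11.2 says the study is not designed to show significant group differences, and SAP 5 calls all analyses exploratory. The staging began as a sentinel safety precaution. Serology runs under one SOP on labels that hide subject and regimen (Protocol 9.2, SAP 4.2.2). Protocol 11 leaves the SAP open until database lock. All of this stands and lowers the severity. It does not remove the point: small samples widen an interval, whereas non-concurrence can move its center. Masked labels protect the assay reading, not the comparability of the people or the product.

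Four stronger readings are tempting and are not supported.

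- A reader might infer that randomization separates nothing the trial compares. That is untrue while stage E is run, because 5v6 is a planned contrast with 10 v 10 randomized together.
- A reader might blame Version 6.0 for all six pairs. Four (1v2, 3v4, 2v6, 4v6) were already non-concurrent in the SAP's own scheme. Version 6.0 adds 1v5 and 3v5 and makes 5v6 mixed.
- A reader might apply the 19-month gap throughout. It does not apply to 1v5 or 3v5.
- A reader might suppose that sera from the two periods were assayed in separate campaigns. The documents give no assay calendar by group.

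Nor should SAP 4.7 be over-read. It says participants are analysed as assigned; it does not assert that every pair was concurrently randomized. The gap is that nothing in the SAP tells the reader otherwise.

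**Conclusion.** The point holds. Six of the seven Table 4.3 contrasts compare groups with no shared enrolment stage, and the seventh is concurrent in 20 of 34 participants at most. For the monovalent vaccines, route and period cannot be separated by any adjustment, because all IM subjects were enrolled by March 2020 and all ID subjects are planned from November 2021. The SAP describes a superseded randomization and attaches plain Fisher p-values to every pair.

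This rests on reading the 36 as three full groups and on stage E being run. The size of any bias is unknown. The rejection and coverage figures show sensitivity to an assumed drift and are not evidence that drift occurred. Table 4.3 is used for the pairs because the pair markers in Tables 4.1 and 4.2 appear displaced in the text available. Given the exploratory aim, this should be fixed before database lock. It does not undermine the primary safety objective.

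**What to change.** 1. In SAP 4.2.1, 4.7 and 9, replace the superseded scheme with the Version 6.0 stages and the ten Group 6 replacements.
2. In Table 4.3, and for the corresponding pairs in Tables 4.1 and 4.2, label 1v2, 3v4, 1v5, 3v5, 2v6 and 4v6 as non-concurrent, non-randomized and descriptive. Report differences with 95% CIs, and add a footnote that these intervals do not cover period bias. Swapping p-values for intervals is not a cure by itself, so the footnote matters.
3. For 5v6, make the concurrently randomized 10 v 10 the primary comparison, with all subjects (12 v 22) as supportive. If the last stage is not run, label 5v6 like the other six.
4. Align the route-superiority sentence in Protocol 4.2 with what these comparisons can show.

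Putting the remaining Group 5 subjects on the list for Groups 1 and 3 is not recommended. It would make 1v5 and 3v5 largely concurrent, but if the Group 6 replacements then followed separately it would remove the only concurrent participants in 5v6. It also cuts against the priority that Protocol 6.2 gives to Groups 1 and 3.

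The cost is SAP and rationale wording, one extra subset analysis, and a weaker claim on the secondary objectives.
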